The sequence will be generated by means of an electronic randomisation system. Said system will be hired by Sophia Laboratories, S.A. of C.V. to a third party. The information corresponding to this third party will be found in the file.

7.4 Blinding (Masking).

Blinding will correspond to the principal investigator and subinvestigator. In addition, the statistical analysis will be carried out in a blinded manner for the final analysis. Blinding can not be guaranteed in the subject.

The masking will be done through the secondary container. The primary packaging will not be masked by the morphological difference between them. The sponsor and the research center will have two teams blinded / not blinded.

They will be identified by means of identical labels. Which, in accordance with current and applicable regulations, must contain at least:

- Name, address and telephone number of the sponsor.
- Pharmaceutical form and route of administration.
- Lot Number.
- Legend "Exclusively for clinical studies"
- Date of Expiry.

7.4.1 Opening of blinding.

Blinding may be opened in the following cases:

1. Presence of a serious adverse event.
2. Safety alarm due to the use of the drugs under study.
3. In case the sponsor determines it for any security reason or other reason that it considers pertinent.
4. In the event that the regulatory authority or ethics committee so rightly requests so as to deem it necessary.

8 Methods. Collection, administration and data analysis.

8.1 Data collection methods.

Clinical monitors will be assigned, who will be authorized to monitor, review, procure and ensure that the quality of the information obtained from the participants is reliable and trustworthy. Each monitor will schedule periodic visits to the research centers in order to review the source documents and corroborate the information captured in the case report format (CRF). All clinical monitors will be trained in relation to the information of the study protocol (objective, visits, procedures, range of accepted values, etc.). In case the data are not identical between the two registers, the clinical monitor will generate a discrepancy, which must be resolved by the research center at the time that the sponsor deems reasonable to meet the objectives of the clinical study. The correction of the discrepancies will be made according to the Good Documentation Practices.

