In the case of self-assessment questionnaires, it is not allowed for the principal investigator or person responsible for filling in to modify what was written by the subject of the study.

The data capture in the investigator's site will be done by the investigator or the designated person of his team after performing the Medical File. The researcher or a designated person of your team will be trained in the filling of the CRF.

All corrections to the CRF data should be made by the investigator or the designated person of your team in accordance with the instructions provided.

To ensure the confidentiality and security of the data, user names and access codes will be used to restrict access to the system only to authorized personnel.

The monitor should ensure that all data has been filled in the CRF. After comparing the data against the source documents, the monitor will ask the researcher to make the correction / clarification using clarifications, so that they are answered and closed as quickly as possible. Once the verification by the monitor is finished, the data will be blocked to avoid modifications.

The Clinical Team of Sophia Laboratories, S.A. of C.V. will give the last medical-scientific review and, if necessary, will unblock data if necessary (request for clarification, opening questions, etc ...) and confirm the freezing of data at the end of the study.

8.3 Statistical methodology.

8.3.1 Analysis of primary and secondary outcome variables.

The statistical analysis will be carried out by personnel of Sophia Laboratories, S.A. of C.V. The SPSS program, versión 19.0, will be used. (IBM Corporation, Armonk, NY, USA).

The designated personnel will be blinded to the intervention groups. The coding will be done using consecutive numbers for each intervention group.

The data will be collected and sorted in an excel sheet. Later they will be exported to the platform of the SPSS program. The variables will be categorized according to their nature.

The results of the continuous quantitative variables will be presented in measures of central tendency: mean, standard deviation and ranges, see table 3 (section 6.4.3).

The Kolmogorov-Smirnov test will be performed to know if the distribution presents normality in the results obtained in each study group [64].

The statistical analysis of the continuous **quantitative variables** to find significant differences (p) will be the following:

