5. Taking the clinical information collected, either during the care provided in the research site or provided by the attending physician (s) in the hospital, the principal investigator records the adverse event in his / her clinical note. of the clinical record stating the seriousness, intensity (mild, moderate or severe), relationship with the product or drug under investigation, as well as,
6. The migration of the relevant data to the case report format and to its respective adverse event section; noting the pertinent information, already referred to in section 9.3.1.1., in virtue of the fact that in cases of serious adverse events, which must be notified in less than 24 hours after the moment in which the principal investigator has knowledge of the same, the clinical monitor of the study is informed, so that in turn it informs the Clinical Team and the Pharmacovigilance Department of the sponsor and later it is informed to the Committee of Ethics in Research. With respect to non-serious adverse events, these will be recorded and adequately addressed and the corresponding regulatory entity will be informed about the safety profile of the IP or investigational medication in the final report of the clinical trial.

The record of the outcome of the adverse event depends substantially on the follow-up that the principal investigator makes to the participant, since it is expected that the majority of harmful phenomena, consult section of the safety profile in number 5.3 and in the researcher's manual, are of a nature ophthalmic, however, there may be systemic alterations. Therefore, in the opinion of the researcher, the withdrawal of the participant or his / her permanence will be considered, according to what is stipulated in section 6.2.1.2 Exclusion criteria of the present research protocol.

9.2.1.4 Causality evaluation.

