The study will not start in the research site if you do not have the confidentiality agreements and economic proposal of each of the principal investigators, duly signed and without having previously obtained the favorable opinion and / or the approval of the Committees of Ethics in Research, Research Committees, and when applicable by the Biosecurity Committee, corresponding.

The study will not begin without having met the relevant local, national or international regulatory requirements and without having the corresponding health authorization.

10.2 Amendments to the protocol.

The amendment procedure will be relevant when there is a need to make any change to a document that is part of the research project or protocol, derived from variations in the methodological structure, substitution of the principal investigator or when identifying risks in the research subjects. The documents subject to amendment will be: protocol, letter of informed consent, researcher's manual, documents for the patient, scales of measurement and schedule of activities.

Any amendment must be approved by the sponsor and / or the principal investigator, the amended document (s), once reviewed and approved by the Research Ethics Committee and the Investigation Committee or when applicable, by the Board of Directors. Biosafety, (entities that issued the initial favorable opinion for the conduct of the investigation) will be sent (s) for authorization by the relevant regulatory entity.

Amendments that substantially modify the protocol, confers an additional or different risk on the research subjects, must be approved by the aforementioned Committees. It is the investigator's responsibility to take action in situations that require immediate action to avoid unnecessary harm to study participants.

The principal investigator has the responsibility to inform the Research Ethics Committee of any amendment to the protocol that could eventually affect the rights, safety or welfare of the research participants. Likewise, he must know any situation or new knowledge that will show a greater risk for the participants, the termination or premature suspension of the study, the reasons and the results obtained up to that moment. You must also inform about the conclusion of the study, when completing the research protocol.

10.3 Early termination of the study.

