The study may be temporarily suspended or terminated prematurely if there is a sufficiently reasonable cause. The written notice, which documents the reason for the suspension or early termination, must be delivered by the executing party of the suspension. The PI must inform the study participants, the CI and the CEI as soon as possible, providing the reasons.

The situations in which the suspension or early termination of the study will be considered include, but are not limited to:

1. Presence of serious adverse events in more than 10% of the participants in each intervention group.
2. The competent authority (COFEPRIS) considered it for security alerts.
3. The Sponsor determined it for your convenience or eventualities such as: economic support, manufacturing errors, etc.
4. Less recruitment than stipulated.
5. Determination of unexpected risks for participants, which are significant or unacceptable.
6. Obtaining new relevant safety information.
7. Insufficient adherence to protocol requirements.
8. The data obtained are not evaluable or are not sufficiently complete.
9. Determination that the primary objective has been reached.
10. Determination of futility.

In case of suspension, the study can be resumed once the situations that led to suspension have been remedied; as long as this justification is sufficient for the sponsor, CI, CEI and regulatory authorities.

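### The only numeric safety trigger for considering suspension (10.3, item 1) refers to *each* group; read literally, an excess of serious adverse events on one product alone does not meet it

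*Combined protocol and SAP*

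**What the plan says.** Section 10.3 opens with a general clause: "The study may be temporarily suspended or terminated prematurely if there is a sufficiently reasonable cause". It then introduces a list of ten items: "The situations in which the suspension or early termination of the study will be considered include, but are not limited to". Item 1 reads "Presence of serious adverse events in more than 10% of the participants in each intervention group".

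Item 1 is the only one of the ten with a figure. The other items that bear on safety have neither a threshold nor a condition on group: item 2 (alerts from the regulator), item 5 ("Determination of unexpected risks for participants, which are significant or unacceptable") and item 6 (new safety information). Item 3, the sponsor's own decision, is equally open.

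Other sections deal with serious adverse events (SAEs) but set no study-level rate:

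- **6.2.1.3** allows an individual subject to be withdrawn after an SAE.
- **7.4.1** lists "Presence of a serious adverse event" among the grounds for opening the blind.
- **9.2.1.3** covers reporting of SAEs, "which must be notified in less than 24 hours after the moment in which the principal investigator has knowledge of the same".
- **9.3.1** requires unanticipated problems that are also SAEs to be reported within 24 hours.
- **10.2** adds: "It is the investigator's responsibility to take action in situations that require immediate action to avoid unnecessary harm to study participants".

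Sections 6.6 and 6.6.1 give 12 subjects per group, 24 in all. Section 7.1 gives 1:1 allocation.

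**The concern.** The trial compares the safety of two travoprost formulations, so SAEs that gather on one product are the pattern a numeric safety trigger most needs to catch. As literally worded, item 1 is met only when both groups exceed 10%, and it stays silent when one group does so alone.

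If item 1 is applied that way, the one item with a figure does not prompt a review of a product-specific excess. Whether suspension is considered then rests on judgement under the unquantified items. The sponsor, the investigator and the committees could also read the same counts differently, because the sentence supports two readings and the protocol does not choose between them.

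**Working it through.** The documents do not derive the 10% threshold, so there is no figure of the plan's own to reproduce. The check turns the threshold into counts and compares the two readings.

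**Inputs.** Threshold: more than 10% (10.3, item 1). Group size: 12 (6.6). The documents give no SAE rate, so every rate below is an assumption.

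**Counts at full enrolment.** 1/12 = 8.3%, which is not above 10%; 2/12 = 16.7%, which is. A group therefore exceeds the threshold at 2 or more of 12.

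- *Each*, read literally: at least 2 of 12 in both groups, so at least 4 subjects. Twelve of 12 against 0 or 1 of 12 fails.
- *Any*: met at 2 of 12 against 0 of 12.

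**Counts during enrolment.** If the percentage is taken over subjects enrolled so far, one SAE exceeds 10% while a group has 9 or fewer subjects (1/9 = 11.1%). It no longer does at 10 (1/10 = 10.0%, not above), so two are needed from 10 to 12. With no SAE in one group, the literal condition cannot be met at any stage, whatever the other group shows. None of this needs an assumed rate.

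**Probabilities at full enrolment.** For one group with true rate p,

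P(X ≥ 2) = 1 − (1−p)^12 − 12p(1−p)^11

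This gives 0.0062 at 1%, 0.0231 at 2%, 0.1184 at 5% and 0.3410 at 10%. Writing a and b for the two groups' values, *each* = ab and *any* = 1 − (1−a)(1−b). For 10% against 1%:

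- *each* = 0.3410 × 0.0062 = 0.0021
- *any* = 1 − 0.6590 × 0.9938 = 0.345

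**Probabilities on a running denominator.** The condition is checked after each subject, with both groups assumed to fill at the same pace. One group never exceeds 10% only if it has no SAE in its first 9 subjects and at most one in its last 3. So

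P(ever above 10%) = 1 − (1−p)^9 [(1−p)^3 + 3p(1−p)^2]

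This gives 0.0868 at 1%, 0.1672 at 2%, 0.3743 at 5% and 0.6234 at 10%. *Any* follows as before. *Each* requires both groups above 10% at the same point and was computed by exact recursion.

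| Assumed SAE rates | Full: *each* | Full: *any* | Running: *each* | Running: *any* |
|---|---|---|---|---|
| 10% v 1% | 0.2% | 34.5% | 5.3% | 65.6% |
| 1% v 1% | 0.004% | 1.2% | 0.7% | 16.6% |
| 2% v 2% | 0.05% | 4.6% | 2.8% | 30.7% |
| 5% v 5% | 1.4% | 22.3% | 13.8% | 60.9% |

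With no risk at all on one product and 20%, 30% or 50% on the other, *any* at full enrolment is met with probability 72.5%, 91.5% and 99.7%. *Each* is met with probability 0 in all three cases.

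**The case against.** **The phrase may only set the denominator.** It can be read as attaching to the participants: percentages are taken group by group, not pooled over 24. On that reading item 1 already says what is wanted. Section 8.3.1 uses the word this way ("The coding will be done using consecutive numbers for each intervention group"), and the both-groups reading leads to a result nobody is likely to have intended. The text is also visibly a rough translation, so the wording may be a loose rendering of *per group*. This is a fair account of probable intent. However, nothing in the document restates item 1 as *any* or *either*, and a numeric trigger should not depend on guessing.

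**The practical consequence is small.** Item 1 mandates nothing and the list is open. Every SAE is reported to the sponsor and the ethics committee, can be unblinded, and may also fall under the unanticipated-problem route in 9.3, which has no group condition. Two SAEs on one product would already have been escalated individually. This stands, and it is why the point is minor. None of these routes supplies the threshold that item 1 was meant to supply.

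**The probabilities are illustrative.** They are, and 10% is a high true rate for healthy adults given one drop a night for 10 days. The core point uses no rate.

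**Changing the word leaves the denominator open.** It remains unclear whether the percentage is over 12 or over subjects enrolled so far, and this matters to the false-prompt rate. The gap exists under either wording and does not undo the correction.

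**Conclusion.** The concern holds, at minor severity. Applied as written, the one quantified safety trigger in 10.3 misses an SAE excess confined to one product, however large: 12 of 12 against 0 or 1 of 12 does not meet it. This follows from the wording and the group size alone.

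The gap between 0.2% and 34.5% at full enrolment rests on assumed rates of 10% and 1%. The running-denominator figures also assume equal filling of the groups and a check after each subject.

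The defect is confined to item 1. It does not mean the study could not be stopped, because the general cause clause, items 2, 3, 5 and 6, the open list and the investigator's duty in 10.2 all remain available. Confidence is medium, because a group-by-group meaning may have been intended.

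**What to change.** In item 1 of section 10.3, replace *each* with *any*, so that the condition is met when more than 10% of participants in any intervention group have an SAE. Leave the 10% threshold and the rest of the list unchanged. If a group-by-group reading was intended all along, the edit only confirms it.

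Compared with the literal reading, the cost is a higher chance that unrelated events prompt a review; the equal-rate rows of the table give its size. At full enrolment the chance is 1.2%, 4.6% and 22.3% for SAE rates of 1%, 2% and 5% in both groups. On subjects enrolled so far it is 16.6%, 30.7% and 60.9%, mostly from a single early SAE. The consequence of a prompt is only that suspension is considered. That is proportionate when one SAE already requires 24-hour notification and permits unblinding.

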10.4 Consent

10.4.1 Obtaining

The informed consent must be obtained before the subject undergoes any procedure indicated in the protocol.

The written consent documents will incorporate the elements of informed consent described in the Declaration of Helsinki and the ICH Guide to Good Clinical Practices and will be in compliance with all applicable laws and regulations.

The PI will provide the potential participant with all the information regarding the characteristics of the study, its potential benefits, risks, objectives and procedures thereof.

This information will be with a language understandable to the subject, it will be explained to the subject that has the right to interrupt their participation in the study at any stage, without affecting the relationship with the researcher and / or future assistance. The informed consent will be put to the consideration of the possible participant; This must have enough time to analyze each and every one of the aspects mentioned above and if there is any doubt this will be clarified by the person in charge of obtaining the informed consent.

Once the participant agrees to participate in the study, he / she must sign and date the letter of informed consent in the presence of two witnesses who have or are not related to the subject of the study, who will participate during the informed consent process and will sign endorse that the process was carried out prior to any study procedure, that the study information was clearly explained and doubts were clarified in case of existing.

If a subject is illiterate, the acceptance will be with their fingerprint, and in the event that the subject is not able to grant an informed written consent, a representative of the subject "legally authorized" can provide such consent. The subject in accordance with the applicable laws and regulations.

The PI must also sign and date this consent.

The informed consent must be signed in duplicate by all involved, and two witnesses, one copy will be filed in the researcher's folder and the other will be delivered to the participant. The PI or delegated personnel, must document the process of obtaining the Informed Consent by means of a detailed medical note, where the signed version is specified, the date on which the document was signed and how the process was carried out.

10.4.2 Special considerations

The auxiliary studies that will be carried out during the conduction of the study (laboratory tests) do not pose an additional risk that should be considered apart from the procedures listed in the informed consent.

10.4.3 Modification to informed consent

Any change to "informed consent" constitutes an amendment to this document and must be presented for approval before the Ethics in Research Committees, and if applicable before the Competent Authorities.

The amendment will include a copy of the new version in the language or languages of the country. Such amendments may be implemented only after obtaining the written approval of the Research Ethics Committee and the Regulatory Entity (as applicable), with the exception of an amendment that is required to eliminate an immediate danger to the subjects of the study.

Each subject affected by the amendment must complete, date and sign two originals of the new version. The subject will be given a signed original of the amendment and the investigator will keep the second original.

In the event that new information may arise that may be relevant to the subject's decision to continue participating in the study, this information should be communicated in a timely manner to the latter. This information will be provided through an amendment to the informed consent, which must be completed, dated and signed in duplicate through a process of re-consent.

10.6 Conflict of interests

The independence of the conduction of the study and its results, of any current or perceived external influence is critical. For this reason, any current conflict of interest of any person who exercises a role in the design, conduct, analysis, publication or any aspect of this study will be declared. Moreover, those people who have a perceived conflict of interest will be asked to handle it in a way appropriate to their participation in the study.

10.6.1 Declaration of interests

The PI commits to make a declaration of financial interests, as well as a conflict of interests prior to the start of the study.

10.7 Access to information

The final database of the study will be owned by Sophia Laboratories, S.A. of C.V. and your access will be restricted. The PI will not have access to it, unless it has prior written authorization from the sponsor.

10.8 Auxiliary care and after the end of the study.

Once the study is finished and the adverse events are closed according to the Adverse events section, the sponsor will not extend care on the research subject.

10.9 Biosecurity aspects.

WITHOUT BIOSECURITY IMPLICATIONS.

The present protocol, with the title: "Phase I clinical study, to evaluate the safety and tolerability of the ophthalmic solution PRO-179 compared with Travatan®, on the ocular surface of clinically healthy subjects", and number: SOPH179-0818 / I NO HAVE BIOSECURITY IMPLICATIONS, since infectious-contagious biological material will NOT be used; pathogenic strains of bacteria or parasites; viruses of any kind; radioactive material of any kind; animals and / or cells and / or genetically modified plants; toxic, dangerous or explosive substances; Any other material that endangers the health or physical integrity of the research center's personnel or the research subjects or affects the environment. It is also stated that cell, tissue or organ transplant procedures or cell therapy procedures will not be carried out in this project, nor will laboratory, farm or wildlife animals be used.

10.10 Final report and publication of results.

10.10.1 Final report.

Once the statistical analysis is finished, a final report will be drafted with the results obtained, in charge of the Clinical Team of the Clinical Operations Department of Sophia Laboratories, S.A. of C.V. Said report will be prepared following the recommendations of the E3 Step 4 Guide of the ICH.

10.10.2 Communication of results.

Regardless of the results in the study, Sophia Laboratories, S.A. of C.V., is committed to communicate to the principal investigators and COFEPRIS, the final report of the study. These results will also be shared with the research committee and the CEI. The communication to the research subjects will be the responsibility of the PI.

Sophia Laboratories, S.A. of C.V. maintain at all times the rights on the publication and disclosure of the information contained.

10.10.3 Publication of results.

